3.1 General analysis principles

Data will be presented at a continental African level. All institutional and national level data will be anonymised prior to publication. Categorical variables will be described as proportions and will be compared using chi-square tests. Continuous variables will be described as mean and standard deviation if normally distributed or median and inter-quartile range (IQR) if not normally distributed. No comparisons between groups will be performed at a univariate level.

For the analysis of the objectives, we will present the following information:

- The number of patients included in each analysis.
- Summary statistics of the outcome (e.g. median (IQR), mean (SD), number (%), range).
- A point estimate, odds ratio or hazard ratio with 95% confidence intervals.
- A two-sided p-value with a significance level of <0.05 will be used where relevant.

For data that are not necessary for each objective, imputation of missing observations will not be made and will be reported descriptively.

Statistical analyses will be performed using the Statistical Package for the Social Sciences (SPSS) version 28.0.1.1 (SPSS Inc., Chicago, IL, USA) and R (version 4.2.1) in RStudio (RStudio Team 2019).

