Statistical analysis plan for Objective 2 “*association between severity of pain and critical illness*”

Data on 'critical illness' will be extrapolated from the parent study ACIOS.

We will conduct univariate and multivariate logistic regression models to determine the association between severity of pain (continuous variable) and critical illness (binary variable). Severity of pain will be the independent variable and critical illness will be the dependent variable. The independent patient associated with critical illness identified in the primary paper will be included in the multivariate model. We will follow best practice by using both visual data analysis and formal modelling to investigate this relationship. The specifics of the models will be determined by the data features to achieve the best fitting model that is interpretable.

We will use a three-level generalized mixed model, with patients being at the first level, hospital at the second and country at the third level, to account for the expected correlation in outcomes within hospitals and countries.

3.7 Statistical analysis plan for Objective 3 “association between severity of pain and mortality”

The defined time for the outcomes is from the point of inclusion of the patient into the study to hospital discharge or death, censored at 7 days. Patients discharged alive are not followed up at home. Patients still in hospital receiving therapy at 7 days will be regarded as “alive” and included in the study.

We will conduct univariate and multivariable logistic regression models to determine the association between severity of pain (continuous variable) and mortality (binary variable). Severity of pain will be the independent variable and mortality will be the dependent variable. Additional patient factors identified in the primary paper to be independently associated with mortality will be included in the multivariate model. We will follow best practice by using both visual data analysis and formal modelling to investigate this relationship. The specifics of the models will be determined by the data features to achieve the best fitting model that is interpretable.

We will use a three-level generalized mixed model, with patients being at the first level, hospital at the second and country at the third level, to account for the expected correlation in outcomes within hospitals and countries.

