A Kaplan-Meier graph will be constructed of the in-hospital mortality from Day 0 to Day 7 for patients with severe (>7 on VAS) pain and patients *without* severe pain (<7 on VAS). Time will be counted from recruitment to the study until discharge, death or censored. The graph will visualise how mortality risk changes over time. A log-rank test for equality of the survival functions will be performed if the assumptions necessary for using the test hold.(Hosmer, Lemeshow et al. 2008)

Missing data: data from patients lost to follow up (missing outcome data) will be included in the statistical analysis without imputation and reported descriptively. Data from these patients will not be included in the mortality analysis (i.e. objective 3), but will be included in other analyses (i.e. objectives 1 and 2).

References

Brennan, F., D. B. Carr and M. Cousins (2007). "Pain Management: A Fundamental Human Right." *Anesthesia & Analgesia* **105**(1): 205-221.

Gan, T. J. (2017). "Poorly controlled postoperative pain: prevalence, consequences, and prevention." *Journal of Pain Research* **10**: 2287-2298.

Hosmer, D. W., S. Lemeshow and S. May (2008). *Applied Survival Analysis: Regression Modeling of Time-to-Event Data*, Wiley.

RStudio Team (2019). *RStudio: Integrated Development Environment for R*. <http://www.rstudio.com/>.

Sinatra, R. (2010). "Causes and Consequences of Inadequate Management of Acute Pain." *Pain Medicine* **11**(12): 1859-1871.

van Boekel, R. L. M., M. C. Warlé, R. G. C. Nielsen, K. C. P. Vissers, R. van der Sande, E. M. Bronkhorst, J. G. C. Lerou and M. A. H. Steegers (2019). "Relationship Between Postoperative Pain and Overall 30-Day Complications in a Broad Surgical Population: An Observational Study." *Annals of Surgery* **269**(5): 856-865.

Wu, C. L. and S. N. Raja (2011). "Treatment of acute postoperative pain." *The Lancet* **377**(9784): 2215-2225.

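### SAP 3.1 both orders chi-square comparisons and bans univariate group comparisons, a log-rank test follows, and no rule says which unadjusted p-values will be reported

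*SAP*

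**What the plan says.** Four instructions in the SAP bear on unadjusted comparisons.

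- Section 3.1, on categorical variables: "Categorical variables will be described as proportions and will be compared using chi-square tests".
- The same paragraph, after a sentence on how continuous variables are summarised: "No comparisons between groups will be performed at a univariate level".
- Objective 2: "We will conduct univariate and multivariate logistic regression models to determine the association" between pain severity and critical illness. Objective 3: "We will conduct univariate and multivariable logistic regression models to determine the association" between pain severity and mortality. Pain is continuous in both. Each section also plans a three-level mixed model (patient, hospital, country).
- Objective 3, Kaplan-Meier paragraph: curves "for patients with severe (>7 on VAS) pain and patients" without it, and then "A log-rank test for equality of the survival functions will be performed if the assumptions necessary for using the test hold".

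On p-values, section 3.1 says only this: "A two-sided p-value with a significance level of <0.05 will be used where relevant". It does not list which analyses carry one.

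**The concern.** The Remit section says the SAP is there to prevent choices made after seeing the data. Where two planned instructions conflict, that protection fails: an analyst could cite section 3.1 for reporting an unadjusted p-value and equally for leaving it out. The Remit's rule that unplanned analyses be labelled does not help, because both instructions are planned. The affected results belong to Objectives 2 and 3, which the Study Summary lists among the primary outcomes.

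The tests in question also suit this cohort poorly. A standard chi-square or log-rank test treats patients as independent, while the SAP expects outcomes to be correlated within hospitals and countries and specifies no clustered version of either test. Both tests pool all adult wards without adjustment, so a difference in case mix between patients with and without severe pain passes straight into the p-value.

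**Working it through.** **The text.** The documents give no sample size, event count or effect size for this sub-study, so there is no figure to reproduce. Each planned analysis can be set against the literal ban:

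| Planned analysis | Unadjusted? | Compares groups? | Conflict with the ban |
|---|---|---|---|
| Chi-square tests (3.1) | yes | yes | direct |
| Log-rank, severe against non-severe pain (Objective 3) | yes | yes, two groups | direct |
| Univariate logistic models (Objectives 2 and 3) | yes | arguable, since pain is continuous | less clear |
| Multivariable models (Objectives 2 and 3) | no | not applicable | none |

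**How far case mix could move a crude result.** Maternal admission serves as the example. Protocol 7.3.3 shows that women in labour are included, and the patient CRF (Appendix 2b) records maternal status. No document gives the maternal share, pain scores or mortality, so every input below is an assumption.

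Let m be the maternal share, pM and pO the proportions with severe pain (maternal, other), and dM and dO the 7-day mortality. Pain and death are unrelated within each stratum (true OR 1). The pooled cells are:

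- severe, died: a = m·pM·dM + (1−m)·pO·dO
- severe, alive: b = m·pM·(1−dM) + (1−m)·pO·(1−dO)
- not severe, died: c = m·(1−pM)·dM + (1−m)·(1−pO)·dO
- not severe, alive: d = m·(1−pM)·(1−dM) + (1−m)·(1−pO)·(1−dO)

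The crude OR is ad/(bc).

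Worked case: m = 20%, pM = 40%, pO = 20%, dM = 0.5%, dO = 5%.

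- a = 0.0004 + 0.0080 = 0.0084
- b = 0.0796 + 0.1520 = 0.2316
- c = 0.0006 + 0.0320 = 0.0326
- d = 0.1194 + 0.6080 = 0.7274
- OR = (0.0084 × 0.7274)/(0.2316 × 0.0326) = 0.81

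Other cases, with pO = 20% throughout:

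| m | pM | dM / dO | Crude OR | Chance that a crude two-proportion test is significant, N = 10,000 |
|---|---|---|---|---|
| any | 20% | any | 1.00 | 5% |
| 10% | 30% | 0.5% / 5% | 0.95 | 7% |
| 20% | 40% | 0.5% / 5% | 0.81 | 39% |
| 30% | 50% | 0.5% / 5% | 0.65 | 93% |
| 30% | 50% | 0.2% / 8% | 0.61 | not computed |
| 20% | 15% | 0.5% / 5% | 1.06 | not computed |
| 20% | 5% | 0.5% / 5% | 1.20 | not computed |

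The N of 10,000 is also assumed, and the last column treats patients as independent. The crude OR runs from 0.61 to 1.20 with no true effect in any row.

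**The case against.** The best defence is that the ban was meant only for descriptive tables. Section 3.1 follows protocol 10.2 closely and has the ban where the protocol allowed t-tests, ANOVA or non-parametric tests. The ban comes straight after the sentence on summarising continuous variables, and Dummy Table 1 has no p-value column. This is a plausible account of the intent, but the SAP does not state it. Even if it did, the chi-square sentence would still need deleting or scoping, and a ban worded without limit would still catch the log-rank test.

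Three further points have force. First, the univariate logistic models regress on a continuous score and can fairly be called associations rather than group comparisons, so that part of the conflict is the weakest. Second, both associations also get multivariable models and a three-level structure, so adjusted results will exist. Whether they adjust for maternal admission cannot be told, because the factors are to come from the primary paper and are not listed. Third, a 95% interval that excludes 1 tells the reader much the same as a p-value, so removing p-values from the univariate odds ratios is partly a matter of labelling. The gain is that the plan says in advance which estimate carries the inference.

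**Conclusion.** The contradiction between the chi-square sentence and the ban, and between the ban and the log-rank test, stands on the text alone and needs no assumption. With p-values reported only where relevant, the SAP lacks a rule for which unadjusted p-values appear. The tests as specified also disregard case mix and the expected clustering. It should be fixed, and the repair is small.

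A reader might infer two stronger things that the documents do not support. One is that maternal patients confound the result strongly and make severe pain look protective. The documents give no figures for that group and do not name it as a confounder. The crude odds ratio can be 1 if maternal pain matches that elsewhere, and above 1 if it is lower. Confounding by case mix is possible, but its size and direction are unknown. The other is that unadjusted results may be reported or dropped at will. The univariate models are firmly prespecified, the log-rank test is conditional only on its assumptions, and the SAP states that it was written before data access. The real discretion lies in the unspecified chi-square tests and in which analyses carry a p-value.

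**What to change.** Make these changes to the SAP:

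1. Delete the chi-square sentence in 3.1.
2. Reword the ban so that it bars unadjusted hypothesis tests between groups, not comparisons of every kind. Univariate odds ratios are then consistent with it.
3. Report the univariate odds ratios for Objectives 2 and 3 as descriptive, with 95% confidence intervals and no p-value.
4. Name the multivariable three-level mixed model as the inference for Objectives 2 and 3.
5. Drop the log-rank test. Keep the day 0 to 7 graph, labelled descriptive and unadjusted. Since the graph stays, a score of exactly 7 also needs a group: the present cut (above 7 against below 7) leaves it in neither.

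Optionally, show the graph and Dummy Table 1 by maternal status as well. The CRF already records it, but the SAP's objectives do not require the split.

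The cost is a few sentences of SAP text and the loss of the unadjusted p-values. No new data are needed.

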3.2 Sample Size / Recruitment

As many sites as possible will be recruited in participating countries. All adult patients will be eligible for inclusion in the sites. A sensitivity analysis will be done for each objective including only data from hospitals that recruited $>90\%$ of eligible patients. We do not have a specific sample size and statistical models will be adapted to the event rates provided by the sample recruited. Participation in the study, and completeness of follow-up will be illustrated by a STROBE flow diagram.

Patient recruitment and description will be presented as follows:

- STROBE flow diagram including i) countries, ii) number of eligible patients, iii) patients included and excluded.
- The number of participating hospitals, hospital characteristics and patients at each hospital level will be reported in a table. Detailed hospital characteristics will be provided in a Supplementary Table.
- The patient characteristics of the cohort will be presented in summary tables.

Objectives

1. To determine patients' self-reported severity of pain in the preceding 24 hours on a scale of 0 – 10.
2. To determine the association between severity of pain and critical illness in adult patients admitted to hospitals across Africa.
3. To determine the association between severity of pain and mortality in adult patients admitted to hospitals across Africa.

Statistical analysis plan for Objective 1 “*self-reported pain severity*”

Using the appropriate summary statistics, we will report patients' self-reported report pain severity in the preceding 24 hours from data collection on a scale of 0 – 10, where 0 is 'no pain' and 10 is 'the worst pain you can imagine'. We will report pain severity across all participants as well as for the following groups: patients with critical illness; patients without critical illness; patients who died; and patients who survived.

Some patients were unable to give pain ratings (e.g. patients who were unconscious at the time of data collection). Therefore, we will also present the number of patients who provided pain reports.

Dummy Table 1. Self-reported pain severity of the African Critical Illness Outcomes Study (ACIOS) patient cohort

	All patients (n=?)	Patients with critical illness (n=?)	Patients without critical illness (n=?)	Patients who died (n=?)	Patients who survived (n=?)
Pain severity (0 – 10) [presented using the appropriate summary statistics]					

Statistical analysis plan for Objective 2 “*association between severity of pain and critical illness*”

Data on 'critical illness' will be extrapolated from the parent study ACIOS.

We will conduct univariate and multivariate logistic regression models to determine the association between severity of pain (continuous variable) and critical illness (binary variable). Severity of pain will be the independent variable and critical illness will be the dependent variable. The independent patient associated with critical illness identified in the primary paper will be included in the multivariate model. We will follow best practice by using both visual data analysis and formal modelling to investigate this relationship. The specifics of the models will be determined by the data features to achieve the best fitting model that is interpretable.

We will use a three-level generalized mixed model, with patients being at the first level, hospital at the second and country at the third level, to account for the expected correlation in outcomes within hospitals and countries.

3.7 Statistical analysis plan for Objective 3 “association between severity of pain and mortality”

The defined time for the outcomes is from the point of inclusion of the patient into the study to hospital discharge or death, censored at 7 days. Patients discharged alive are not followed up at home. Patients still in hospital receiving therapy at 7 days will be regarded as “alive” and included in the study.

We will conduct univariate and multivariable logistic regression models to determine the association between severity of pain (continuous variable) and mortality (binary variable). Severity of pain will be the independent variable and mortality will be the dependent variable. Additional patient factors identified in the primary paper to be independently associated with mortality will be included in the multivariate model. We will follow best practice by using both visual data analysis and formal modelling to investigate this relationship. The specifics of the models will be determined by the data features to achieve the best fitting model that is interpretable.

We will use a three-level generalized mixed model, with patients being at the first level, hospital at the second and country at the third level, to account for the expected correlation in outcomes within hospitals and countries.

A Kaplan-Meier graph will be constructed of the in-hospital mortality from Day 0 to Day 7 for patients with severe (>7 on VAS) pain and patients *without* severe pain (<7 on VAS). Time will be counted from recruitment to the study until discharge, death or censored. The graph will visualise how mortality risk changes over time. A log-rank test for equality of the survival functions will be performed if the assumptions necessary for using the test hold.(Hosmer, Lemeshow et al. 2008)

Missing data: data from patients lost to follow up (missing outcome data) will be included in the statistical analysis without imputation and reported descriptively. Data from these patients will not be included in the mortality analysis (i.e. objective 3), but will be included in other analyses (i.e. objectives 1 and 2).

References

Brennan, F., D. B. Carr and M. Cousins (2007). "Pain Management: A Fundamental Human Right." *Anesthesia & Analgesia* **105**(1): 205-221.

Gan, T. J. (2017). "Poorly controlled postoperative pain: prevalence, consequences, and prevention." *Journal of Pain Research* **10**: 2287-2298.

Hosmer, D. W., S. Lemeshow and S. May (2008). *Applied Survival Analysis: Regression Modeling of Time-to-Event Data*, Wiley.

RStudio Team (2019). *RStudio: Integrated Development Environment for R*. <http://www.rstudio.com/>.

Sinatra, R. (2010). "Causes and Consequences of Inadequate Management of Acute Pain." *Pain Medicine* **11**(12): 1859-1871.

van Boekel, R. L. M., M. C. Warlé, R. G. C. Nielsen, K. C. P. Vissers, R. van der Sande, E. M. Bronkhorst, J. G. C. Lerou and M. A. H. Steegers (2019). "Relationship Between Postoperative Pain and Overall 30-Day Complications in a Broad Surgical Population: An Observational Study." *Annals of Surgery* **269**(5): 856-865.

Wu, C. L. and S. N. Raja (2011). "Treatment of acute postoperative pain." *The Lancet* **377**(9784): 2215-2225.

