**2b: Patient's bedside CRF**

**African Critical Illness Outcomes Study (ACIOS) – Patient CRF**

**Clinical assessment**

Date of assessment:

Vital signs done by the investigating team:  Y  N If no, specify  Vital signs from patient records  Not done

Position of patient:

Lying flat on back(<30°)  Lying on side  Head-up(30°-60°)  Sitting(>60°)  Head-down  Other

Airway patency:  Normal  Partial obstruction  Complete obstruction

Conscious level (AVPU):  Alert  Responds to Voice  Responds to Pain  Unresponsive

Heart rate  /min Oxygen saturation  % Respiratory rate  /min

Systolic blood pressure  /mmHg Diastolic blood pressure  /mmHg

Currently receiving IV fluids  Y  N Receiving oxygen (now)  Y  N

Receiving vasopressor/inotrope (now)  Y  N Airway action (now)  Y  N

Circle the worst pain you had in the last 24 hours: 0 (no pain) 1 2 3 4 5 6 7 8 9 10 (worst pain you can imagine)

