Primary outcomes	
 1. To determine patients’ self-reported severity of pain in the preceding 24 hours on a scale of 0 – 10. 2. To determine the association between severity of pain and critical illness in adult patients admitted to hospitals across Africa. 3. To determine the association between severity of pain and mortality in adult patients admitted to hospitals across Africa.
Data collection duration	One day in each hospital in September-December 2023 plus 7 days follow-up in each hospital
Proposed start date	7 th September 2023
Proposed end date	27 th December 2023

Introduction

Pain is poorly managed in hospitalised patients (Wu and Raja 2011). Uncontrolled pain in hospitalised patients is strongly associated with both short- and long-term complications. Patients are more likely to develop secondary complications such as sepsis, bleeding, and infarctions if their pain is not adequately managed (Brennan, Carr et al. 2007, van Boekel, Warlé et al. 2019). Further, pain of >7 on a visual analogue scale is strongly associated with an increased risk of persistent pain (Sinatra 2010). In high-income countries, up to 86% of hospitalised patients report having poorly managed pain (Wu and Raja 2011, Gan 2017). However, there is a paucity of the literature on the severity of acute pain in hospitalised patients in Africa. Therefore, this sub-study aims to determine the severity of self-reported pain in hospitalised patients across Africa; and the relationship between severity of pain and (1) critical illness and (2) mortality. This study falls under the ACIOS – African Critical Illness Outcome Study – parent study.

2. Statistical Analysis Plan

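### The Kaplan-Meier pain groups (>7 versus <7) leave a score of exactly 7 in neither group

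*SAP*

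**What the plan says.** SAP section 3.7 plans a Kaplan-Meier graph of in-hospital mortality from Day 0 to Day 7 in two groups: "patients with severe (>7 on VAS) pain and patients *without* severe pain (<7 on VAS"). The same groups feed a log-rank test, which "will be performed if the assumptions necessary for using the test hold".

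The pain item on the patient CRF (Protocol Appendix 2b) asks the patient to circle one number on a printed row: "0 (no pain) 1 2 3 4 5 6 7 8 9 10 (worst pain you can imagine"). The SAP's first objective uses the same 0 to 10 range.

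The only other mention of the cut-off is in the SAP Introduction, as background: "pain of >7 on a visual analogue scale is strongly associated with an increased risk of persistent pain". That sentence does not say where a score of 7 goes, and nothing else in either document does.

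The other pain analyses do not use the cut-off. For Objective 1: "We will report pain severity across all participants as well as for the following groups", these groups being defined by critical illness and by survival. The Objective 3 regression examines the "association between severity of pain (continuous variable) and mortality (binary variable"), and the Objective 2 model also takes pain as continuous.

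**The concern.** A two-group survival comparison needs a rule that places every patient with a valid exposure value. Here both inequalities exclude the boundary. On a true visual analogue scale, read as a continuous length, a value of exactly 7 would be rare and the gap would hardly matter. On the scale collected, 7 is a full response category.

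Two things can follow:

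- **The text is followed literally.** Objective 3 is then reported on different sets of patients. The logistic models include the 7s, while the graph and log-rank test omit them. The missing-data paragraph in section 3.7 removes patients from the mortality analysis only for missing outcome data. It gives no reason to remove someone with a recorded score and a known outcome.
- **The analyst notices the gap and places the 7s.** That choice would then be made after data access, and the SAP's remit says the document exists to prevent decisions of that kind.

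The effect on the survival contrast could go either way. It depends on how mortality varies with pain, on which the documents give no data.

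**Working it through.** The plan states no sample size, event count or pain distribution, so it has no figure of its own to reproduce. The check applies the two stated inequalities to the values the CRF allows, then sizes the gap under stated assumptions.

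**Step 1: which scores are placed.** Allowed values (CRF): 0, 1, …, 10, which is 11 values.

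| Rule | Severe | Without severe pain | Unplaced |
|---|---|---|---|
| As written: >7 versus <7 | 8, 9, 10 | 0–6 | 7 |
| >7 versus ≤7 | 8, 9, 10 | 0–7 | none |
| ≥7 versus <7 | 7, 8, 9, 10 | 0–6 | none |

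One of the 11 response values is unplaced as written. Either closed rule places all 11.

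**Step 2: how many patients.** Let p7 be the share of raters scoring 7 and p8 the share scoring 8–10. Neither is in the documents. Assumed ranges: p7 = 3–15%, p8 = 10–30%.

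Unplaced per 1,000 raters = 1,000 × p7:
- low: 1,000 × 0.03 = 30
- high: 1,000 × 0.15 = 150

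**Step 3: weight of the 7s in the group they would join.**

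If they join the comparator (0–7), their share is f = p7 / (1 − p8):
- low: 0.03 / 0.90 = 3.3%
- high: 0.15 / 0.70 = 21.4%

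If they join the severe group (7–10), their share is p7 / (p7 + p8):
- low: 0.03 / (0.03 + 0.30) = 0.03 / 0.33 = 9%
- high: 0.15 / (0.15 + 0.10) = 0.15 / 0.25 = 60%

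**Step 4: effect on crude comparator mortality.** Let m7 be mortality among the 7s and m06 mortality among the 0–6s. With the 7s included, comparator mortality is (1 − f) × m06 + f × m7. Without them it is m06. The change from leaving them out is therefore −f × (m7 − m06).

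For an assumed absolute difference of 2 percentage points:
- low: 0.033 × 2 = 0.07 points
- high: 0.214 × 2 = 0.43 points

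The sign is opposite to that of m7 − m06, which is unknown. If the two mortalities are equal, the change is zero.

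**Step 5: other analyses.** The Objective 1 summaries and the Objective 2 and 3 logistic models do not use the cut-off. The change in their estimates is nil.

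**The case against.** There are five fair points on the other side.

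- **The intent is probably clear.** Describing the second group as being without severe pain makes it the complement of the first, so the sign is likely a slip for ≤7 and not an instruction to drop patients. This is plausible. The symbol still contradicts the words beside it, and someone programming from the symbol would lose the 7s.
- **A reader could detect the loss.** SAP section 3.1 promises the number of patients in each analysis, so a missing category should show as a smaller count. The multivariable cohort may also differ from the graph's because of missing covariates. Both are true, but a smaller count would show the loss without justifying it.
- **The documents do not strictly settle which sign to change.** Keeping <7 and changing >7 to ≥7 also closes the gap, and Step 3 shows that choice would weigh more heavily on the severe group. This stands as a caution. The balance favours >7: the SAP attaches that threshold to severe pain in section 3.7, repeats it in the Introduction, and words the other group as the remainder. The Introduction's support is limited, since it concerns persistent pain and not mortality.
- **The figures rest on assumptions.** They do. The 0.07–0.43 range describes crude mortality under one of two possible closures. It does not bound the effect on the curves or the log-rank statistic.
- **A sign could have been lost when the PDF was converted to text.** This cannot be fully excluded, but nothing in the text suggests it, and the authors can check quickly.

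None of these places a score of 7.

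**Conclusion.** The point holds as a minor correction. As written, the grouping omits one of the 11 possible pain scores from the Kaplan-Meier graph and the log-rank test. That follows directly from the SAP and the CRF and needs no assumption.

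The practical size is unknown, and the ranges in the working illustrate it only under the assumed score distribution and the assumed 2-point mortality difference. The direction is also unknown.

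The damage is confined to a supporting graph and to a test that is itself conditional on its assumptions. The main Objective 3 result, from logistic models with continuous pain, is untouched.

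**What to change.** Amend the one sentence in SAP section 3.7:

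1. Keep severe pain as >7 (scores 8–10) and define the comparator as ≤7 (scores 0–7), so that every recorded score is placed.
2. Replace the VAS label with the instrument used: the 0–10 whole-number rating of worst pain over the previous 24 hours. The label does not place the 7s by itself, but it hides the fact that 7 is a full category.

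A sensitivity plot with ≥7 versus <7 is optional and would show whether the picture depends on where the 7s sit. If the authors intended ≥7 as severe, they should state that rule instead; what matters is one exhaustive rule. If the analysis has already been run, the report should say how scores of 7 were handled.

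The cost is two wording edits in one sentence, with no new data and no required extra analysis.

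### The Kaplan-Meier graph of in-hospital death stops time at live discharge, a competing event, so its level overstates 7-day in-hospital mortality

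*SAP*

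**What the plan says.** SAP section 3.7 (Objective 3) describes the graph: "A Kaplan-Meier graph will be constructed of the in-hospital mortality from Day 0 to Day 7", for patients with and without severe pain. It sets the time scale: "Time will be counted from recruitment to the study until discharge, death or censored". It states the purpose: "The graph will visualise how mortality risk changes over time". It attaches a conditional test: "A log-rank test for equality of the survival functions will be performed if the assumptions necessary for using the test hold".

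The same section defines outcome time as running "from the point of inclusion of the patient into the study to hospital discharge or death, censored at 7 days", and adds: "Patients discharged alive are not followed up at home". Section 8 of the protocol defines the event as death in hospital. Section 7.3.4 lists three outcome states: discharged alive, dead, or alive and still in hospital at 7 days.

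The main analysis of Objective 3 is a logistic model: "Severity of pain will be the independent variable and mortality will be the dependent variable". Patients with missing outcome are left out: "Data from these patients will not be included in the mortality analysis (i.e. objective 3"). Neither document mentions competing risks, cumulative incidence, or keeping discharged patients at risk to day 7.

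**The concern.** Kaplan-Meier censoring assumes that a censored patient could still have the event later, at the same rate as those who remain. That cannot hold here: the event is death in hospital, and a patient who has gone home alive cannot have it. Removing that patient from the risk set leaves each later death to be divided by a smaller denominator. The curve then estimates mortality as if nobody could be discharged, which is not the risk the SAP says the graph will show.

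Three things are at stake.

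- **Level.** The day-7 height of each curve is likely to be read as 7-day in-hospital mortality, and it will usually be too high.
- **Comparison.** If patients with severe pain leave hospital sooner or later than the others, the excess differs between the curves. They can separate, or draw together, because of discharge alone.
- **Consistency.** On the natural coding, the binary mortality outcome counts a live discharge as a survivor. The graph removes the same patient from the risk set, so the two displays in one objective would imply different 7-day mortality.

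**Working it through.** **Inputs.** The documents give no mortality, discharge rate, sample size or group split for this graph, so there is no planned figure to reproduce. The structure comes from SAP section 3.7: time ends at discharge, death or day 7, and patients lost to follow-up are excluded. Live discharge is therefore the only source of censoring before day 7. All rates below are assumptions. Write d for the proportion dead and q for the proportion discharged alive by day 7.

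**Step 1: direction.** Take 10 patients, with 5 discharged on day 1 and 1 death on day 3. Five remain at risk on day 3, so 1-KM = 1/5 = 20%. The observed proportion is 1/10 = 10%, and the Aalen-Johansen estimate is also 10%. In 50,000 random datasets analysed in exact fractions, 1-KM exceeded deaths/n in every dataset where a death fell on a later day than a live discharge, and equalled deaths/n in all the others. Deaths on the same day as the first discharge add no excess, because the usual tie rule counts deaths first.

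**Step 2: whole-day example.** Take 1,000 patients, 50 deaths and 500 discharges (72, 72, 72, 71, 71, 71, 71 on days 1 to 7), with deaths counted before discharges each day. The observed proportion is 5.0% throughout.

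| Deaths on days 1 to 7 | 1-KM at day 7 |
|---|---|
| 7, 7, 7, 7, 7, 7, 8 (even) | 6.7% |
| 20, 12, 7, 5, 3, 2, 1 (early) | 5.7% |
| 50 on day 1 | 5.0% |

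In the even case the numbers at risk are 1000, 921, 842, 763, 685, 607 and 529. The survival product is (1 - 7/1000)(1 - 7/921)...(1 - 8/529) = 0.9330.

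**Step 3: continuous-time models.**

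- *Constant hazards.* The total cumulative hazard is -ln(1 - d - q), and the share d/(d + q) is death. For d = 0.05 and q = 0.50: -ln(0.45) = 0.7985; 0.7985 × 0.05/0.55 = 0.0726; 1-KM = 1 - exp(-0.0726) = 7.0%, a ratio of 1.40 to the true 5%.
- *Early deaths.* Death density is proportional to exp(-0.5t) on 0 to 7 days (half the deaths by day 1.3), with uniform discharge. Then 1-KM = 1 - exp(-∫ f_death/S_overall dt), where S_overall is the proportion still alive in hospital. For the same d and q this gives 5.9%, a ratio of 1.18.

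Over d from 3% to 20% and q from 30% to 65%, the ratio runs from 1.19 to 1.80 with constant hazards and from 1.09 to 1.32 with early deaths.

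**Step 4: the log-rank test.** Rejection rates were simulated at two-sided 5% with 8,000 v 2,000 patients (10,000 replicates for the 50% v 65% and 50% v 35% rows, 4,000 for the others).

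| Dead by day 7 | Discharged by day 7 | Discharge censored: constant / early deaths | Discharged kept at risk: constant / early deaths |
|---|---|---|---|
| 8% v 8% | 50% v 50% | 5% / 5% | 5% / 5% |
| 8% v 8% | 50% v 55% | 10% / 6% | 5% / 6% |
| 8% v 8% | 50% v 60% | 28% / 8% | 6% / 5% |
| 8% v 8% | 50% v 65% | 53% / 11% | 5% / 6% |
| 8% v 10% | 50% v 35% | 26% / 60% | 80% / 80% |

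In the 50% v 65% row, the ratio of day-7 cumulative hazards of death is 1.20 (constant) or 1.08 (early), although mortality is equal. These rejections reflect a real difference in the hazard of death among patients still in hospital. They are not false positives of the log-rank test; they answer a different question from 7-day mortality.

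**The case against.** **The SAP never says that discharge is censored.** It lists discharge next to death and censoring. But the alternatives fail: counting discharge as the event would not plot mortality, and carrying discharged patients to day 7 contradicts the sentence that ends time at discharge. If either was intended, the sentence still has to change.

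**The coding of live discharges as survivors in the logistic model is also inferred.** This is correct. Section 3.7 says explicitly only that patients still in hospital at day 7 count as alive. The outcome categories in the protocol and the CRF make survivor coding the natural reading. The mismatch with the graph, and the statement that the logistic model is unaffected, both rest on it.

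**The log-rank test is valid for the in-hospital hazard, and the SAP does not say that it compares 7-day proportions.** This also stands. What remains is a caution about interpretation. The simulated rates depend heavily on assumed group sizes, discharge gaps and death timing: at 50% v 65% discharged, rejection falls from 53% to 11% when deaths come early.

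**The excess may be small.** This is possible. It is zero if no death falls on a later day than a live discharge in the same group, and modest if deaths cluster early. SAP section 3.1 also promises number and percentage summaries, so the crude proportion may appear beside the graph. That would expose the discrepancy without correcting the curve.

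**Conclusion.** The concern holds. Carried out as written, the graph censors a competing event, and its level is not the in-hospital mortality risk it is said to show. The upward direction follows from the estimator once any death in a group falls on a later day than a live discharge, which is very probable in a large cohort. The size is unknown: under the assumed inputs the ratio of 1-KM to the observed proportion runs from 1.09 to 1.80, and it is 1.00 in the limiting case.

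The scope is one supporting graph and its conditional test, unadjusted for hospital and country. The three-level logistic model, which carries the Objective 3 association, is not affected provided live discharges are coded as survivors. It should still be fixed, because the association with mortality is one of the sub-study's three listed primary outcomes and this is its only planned time-to-event display.

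**What to change.** Amend the Kaplan-Meier paragraph in SAP section 3.7:

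1. Plot the Aalen-Johansen cumulative incidence of in-hospital death by pain group, with live discharge as a competing event. Alternatively, keep patients discharged alive event-free in the risk set to day 7. Either way, each curve ends at that group's observed 7-day in-hospital death proportion.
2. For the comparison, rely on the three-level logistic model. If a test is wanted with the graph, use Gray's test, or a log-rank test with discharged patients kept at risk to day 7, and label it as unadjusted for hospital and country.
3. If the planned log-rank test is kept, label it as a comparison of the hazard of death while in hospital, not of 7-day mortality.
4. State that patients discharged alive are coded as survivors in the binary mortality outcome.

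The cost is a few lines of SAP text and a different function in R, which the SAP already names. No new data are needed: the follow-up section of the patient CRF (protocol Appendix 2b) records day-7 status and the date of discharge or death.
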